2.1.2 Definition of terms included in study endpoints

Efficacy endpoints

eDiary Day

A day in which a subject uses the eDiary.

Migraine Day

A migraine day is defined as any calendar day in which the patient experiences a qualified migraine headache (onset, continuation, or recurrence of the migraine headache). A qualified migraine headache ([IHS, 2013](#)) is defined as a migraine with or without aura, lasting for ≥ 30 minutes, and meeting at least one of the following criteria:

1. ≥ 2 of the following pain features:
 - Unilateral
 - Throbbing
 - Moderate to severe
 - Exacerbated with exercise/physical activity
2. ≥ 1 of the following associated symptoms:
 - Nausea and/or vomiting
 - Photophobia and phonophobia

If the patient took a migraine-specific medication (ie, triptan or ergotamine) during aura, or to treat a headache on a calendar day, then it will be counted as a migraine day regardless of the duration and pain features/associated symptoms.

Monthly Migraine Days

Number of migraine days between each monthly IP dose that are normalized in a 28-day interval. Monthly migraine days at baseline are the number of migraine days in the baseline period that are normalized in a 28-day interval. Days without eDiary data in each normalized monthly interval will be prorated. All details of calculation are in [Section 5.1.2](#) (The same proration method will be applied for other efficacy endpoints thereafter).

Achievement of at least a 50% reduction from baseline in monthly migraine days in the last month of the double-blind treatment epoch

Calculated based on the following: $(\text{monthly migraine days in the last month of the DBTE} - \text{baseline monthly migraine days}) * 100 / \text{baseline monthly migraine days}$ is less than or equal to - 50%

[REDACTED]

[REDACTED]

Headache Day

A headache day is any calendar day in which the subject experiences a qualified migraine or non-migraine headache (initial onset, continuation or recurrence of the headache). A qualified headache is defined as:

- a qualified migraine headache (including an aura-only event that is treated with acute migraine-specific medication), or
- a qualified non-migraine headache, which is a headache that lasts ≥ 30 minutes and is not a qualified migraine headache, or
- a headache of any duration for which acute headache treatment is administered.

Monthly Headache Days

Number of headache days between each monthly IP dose. Monthly headache days at baseline are the number of headache days in baseline period. Days without eDiary data in each monthly interval are handled by proration according to [Section 5.1.2](#).

Monthly Acute Headache Medication Treatment Days

Number of days on which acute headache medications are used as recorded in eDiary between each monthly IP dose. Monthly acute headache medication treatment days at baseline are the number of acute headache medication treatment days in the baseline period. Days without eDiary data are handled by proration according to [Section 5.1.2](#).

[REDACTED]

[REDACTED]

Monthly Acute Migraine-Specific Medication Treatment Days

Number of days on which acute migraine-specific medications are used as recorded in eDiary between each monthly IP dose. Migraine-Specific medications include two categories of medications: triptan-based migraine medications and ergotamine-based migraine medications. Monthly migraine-specific medication use at baseline is the number of migraine-specific medication treatment days in the baseline period. Days without eDiary data are handled by proration according to [Section 5.1.2](#).

Change from baseline in monthly acute migraine-specific medication treatment days in the last month of the double-blind treatment epoch

Calculated based on the following: (monthly acute migraine-specific medication treatment days in the last month of the DBTE) – (baseline monthly acute migraine-specific medication treatment days)

Response

At least 50% (or 75%, 100%) reduction from baseline in monthly migraine days.

[REDACTED]

[REDACTED]

[REDACTED]

[REDACTED]

[REDACTED]

Migraine Physical Function Impact Diary (MPFID)

The Migraine Physical Function Impact Diary (MPFID) is a self-administered 13-item instrument measuring physical functioning. It has two domains, Impact on Everyday Activities (7 items) and Physical Impairment (5 items), and one stand-alone global question which provides an assessment of overall impact on everyday activities. Subjects respond to items using a 5-point scale, with difficulty items ranging from “Without any difficulty” to

“Unable to do” and frequency items ranging from “None of the time” to “All of the time.” These are assigned scores from 1 to 5, with 5 representing the greatest burden. For each domain, the scores will be calculated as the sum of the item responses and the sum will be rescaled to a 0 - 100 scale, with higher scores representing greater impact of migraine (ie, higher burden). There will be a score for each of the two domains and a third score for the stand-alone item. The recall period is the past 24 hours. Please refer to [Section 2.10](#) and [Appendix E.1](#) for details.

Subjects will complete the MPFID every day using the eDiary during DBTE.

Monthly average MPFID score is defined as the sum of observed MPFID scores divided by the total number of observed MPFID scores between each monthly IP dose. Monthly average MPFID score at baseline is the average MPFID score in the baseline period.

Change from baseline in monthly average physical impairment scores as measured by the MPFID in the last month of the double-blind treatment epoch

Calculated based on the following: (monthly average physical impairment scores as measured by the MPFID in the last month of the DBTE) – (baseline monthly average physical impairment scores as measured by the MPFID)

Change from baseline in monthly average impact on everyday activities scores as measured by the MPFID in the last month of the double-blind treatment epoch

Calculated based on the following: (monthly average impact on everyday activities scores as measured by the MPFID in the last month of the DBTE) – (baseline monthly average impact on everyday activities scores as measured by the MPFID)

[REDACTED]

[REDACTED]

[REDACTED]

[REDACTED]

[figure not shown]
[REDACTED]

[figure not shown]
[REDACTED]

[Redacted]

[Redacted]

[Redacted]

Safety Endpoints

Treatment-Emergent Adverse Event (TEAE)

Adverse Events (AEs) recorded on the Adverse Events eCRF page that occurs on or after first dose of investigational product as determined by the flag indicating if the adverse event started prior to the first dose on the Adverse Events eCRF and up to and including 112 days after the end of IP (16 weeks after the last dose of IP).

Serious Adverse Event (SAE)

SAEs determined by the flag indicating if the adverse event is serious on the Adverse Events eCRF page will include those that occur after signing of the informed consent and up to and including end of study.

Serious Treatment-Emergent Adverse Event

A serious treatment-emergent adverse event is an SAE considered to be treatment-emergent.

Treatment-Related Adverse Event

A treatment-related AE is defined as a treatment-emergent adverse event that is considered by investigators to have reasonable possibility that it may have been caused by IP as determined

by the flag indicating that there is a reasonable possibility that the AE is related to investigational product on the Adverse Events eCRF page.

Serious Treatment-Related Adverse Event

A serious treatment-related adverse event is an SAE considered to be treatment-related.

Treatment-Emergent Adverse Event of Special Interest

A treatment-emergent adverse event of special interest (EOI) is one of scientific and medical concern specific to the sponsor's product or program, for which ongoing monitoring and rapid communication by the investigator to the sponsor may be appropriate. Such events may require further investigation in order to characterize and understand them. Predefined search strategies such as standardized MedDRA queries (SMQ) or Novartis defined queries may be applied to EOIs. The EOI search list is a living document and will be updated in response to the emerging safety profile of AMG 334.

Columbia-Suicide Severity Rating Scale (C-SSRS)

The Columbia-Suicide Severity Rating Scale (C-SSRS) is a questionnaire that prospectively assesses Suicidal Ideation and Suicidal Behavior. The C-SSRS must be administered at each visit, including unscheduled visits.

Two versions depending on the type of visits will be used in this study: Life-time and Since Last Visit. The C-SSRS consists of a maximum of 20 items to evaluate suicidal behavior and suicidal ideation.

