The exposure- adjusted subject incidence rate for a given event in a given period is defined as the number of subjects with at least one reported occurrence of the event in a given time period divided by total subject years at risk in that period. The time at risk for each subject will differ for each adverse event. For subjects with events, only the time until the first event contributes to the total subject years at risk. For subjects who do not experience the event, the time at risk will be calculated based on the safety analysis study window. This rate will be presented per 100 subject years. For subjects with multiple occurrences of the same event, the event will be only counted once per subject.

Time at risk

The time at risk matches the time generally considered for safety summaries except SAEs. In particular, it will be used in the analysis of adverse events to derive (exposure-adjusted) incidence rates.

Prior and concomitant medication

Prior medication will be defined as any non-study medication taken prior to the first dose of the randomized study medication, irrespective of whether the medication continued into the treatment period.

Any non-study medication administered at least once between the day of first dose of randomized study medication and end of the study will be a concomitant medication.

Analysis windows

In general, by-visit analyses, including evaluable scheduled and unscheduled data, will be conducted using analysis windows. Analysis windows will align with the scheduled visit day for each assessment and have its lower and upper bounds symmetrically between the analysis window midpoints (i.e. the scheduled visit day for the particular assessment).

For efficacy parameters: In case of multiple assessments within a analysis window, the scheduled visit will be used regardless of the distance from the target day. Unscheduled visit will only be used when there is no measurement from the scheduled visit in the defined window. In that case the assessment value closest to the scheduled visit day will be used. In case of equal distances, the latest assessment value will be used. The exception is an assessment at early study withdrawal visits along with another assessment within a window. In such cases the early-withdrawal assessment will be used.

For safety parameters: in case of competing assessments within a analysis window, the last one closest to the scheduled visit day will be used.

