Study visit	Target Day	Study Day for vital signs, C-SSRS (for lab [REDACTED] include only Day1, Week 12, 24, 64)	Study Day [REDACTED]
Baseline	Please refer to Section 2.1.1		
Day 1	1	1	1
Week 4	29	16-43	16-43
Week 8	57	44-71	44-71
Week 12	85	1.72 to (week 12 OLTE dose date) for subjects who receive OLTE dose at week 12 2.72-99 for subjects who did not receive OLTE dose at week 12	1.72 to (week 12 OLTE dose date) for subjects who receive OLTE dose at week 12 2.72-99 for subjects who did not receive OLTE dose at week 12

For safety analyses which are summarized by study phase, analysis windows will be set up based on study phase:

Table 4 Study Phases for Safety analysis

Study Phase	Start Time Point	End Time Point
Double-blind Treatment Epoch	Study Day 1 (after the 1st DB IP Dose)	
 • First OLTE Dose Date - 1 for subjects receive OLTE IP dose; • MIN(EoS Date, last IP dose date + 84 days) for subjects did not receive any OLTE IP dose

Note: all anti-AMG 334 antibody data during all epochs will be included in immunogenicity analysis.

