2.7.1 Adverse events (AEs)

The Medical Dictionary for Regulatory Activities (MedDRA) version 18.0 or later will be used to code all adverse events (AE) to a system organ class (SOC) and a preferred term (PT). All adverse events will be graded using the Common Terminology Criteria for Adverse Events (CTCAE) Version 4.03 (see details in [Section 5.2](#)). All adverse event tables will be summarized by treatment group.

AE tables by SOC and PT (and grade), will be sorted alphabetically by SOC and then descending order of frequency based on the AMG 334 140 mg dose by PT within each SOC. AE tables by preferred term only will be sorted in descending order of frequency based on the AMG 334 140 mg dose, then the placebo dose and then alphabetically.

Overall subject incidence of AEs will be summarized for all treatment-emergent AEs (TEAEs), serious AEs, AEs leading to withdrawal of IP, and fatal AEs for the DBTP.

Subject incidence of all TEAEs, serious AEs, AEs leading to withdrawal of IP, serious AEs leading to withdrawal of IP, fatal AEs will be tabulated by SOC and PT for the DBTE.

In addition, subject incidence of all treatment-emergent AEs and serious AEs will be tabulated by SOC, PT and CTCAE grade for the DBTE.

Subject incidence and exposure-adjusted subject incidence of all TEAEs and serious AEs will be tabulated by PT in descending order of frequency for the DBTE.

Treatment-related treatment-emergent AEs will be summarized for DBTE by SOC, PT and CTCAE grade.

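### The SAP gives conflicting windows for the by-arm double-blind SAE tables, and the exposure-adjusted SAE rate can end up with a numerator and denominator from different periods

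*SAP*

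**What the plan says.** SAP 2.1.2 defines SAEs without a first-dose condition: they "will include those that occur after signing of the informed consent and up to and including end of study". It then defines a narrower set: "A serious treatment-emergent adverse event is an SAE considered to be treatment-emergent".

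SAP 2.7.1 states that "All adverse event tables will be summarized by treatment group". It lists serious AEs, not serious treatment-emergent AEs, in the overall double-blind summary, in the tables by system organ class and preferred term, in the tables by CTCAE grade, and in the rate table: "Subject incidence and exposure-adjusted subject incidence of all TEAEs and serious AEs will be tabulated by PT in descending order of frequency for the DBTE".

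SAP 2.1.1 defines the denominator of the exposure-adjusted rate. For patients without the event, "the time at risk will be calculated based on the safety analysis study window". For the others, "For subjects with events, only the time until the first event contributes to the total subject years at risk". Its time-at-risk paragraph adds: "The time at risk matches the time generally considered for safety summaries except SAEs".

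Table 4 in the same section sets windows for safety analyses summarised by study phase. The double-blind phase opens on Study Day 1, once the first double-blind dose has been given. It closes the day before the first open-label dose or, for patients who never receive one, at the earlier of end of study and 84 days after the last dose. The treatment-emergent definition in SAP 2.1.2 runs to 112 days after the end of study drug.

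**The concern.** The SAP has a term for SAEs that arise on treatment but does not use it in the tables that compare the arms. In the same sentences it applies the treatment-emergent limit to AEs in general and names serious AEs beside them. The exception for SAEs in the time-at-risk paragraph suggests that SAEs are meant to be counted over a different period from the one used for the denominator, yet a rate per time at risk is still requested for them.

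Two competent programmers could therefore produce different SAE tables. One would apply Table 4 and drop events before the first dose. The other would apply the SAE definition and keep them, under an arm whose drug the patient had not yet received. The same definition runs to the end of the study, so open-label SAEs could also fall under the original arm. SAE counts in a 12-week trial of this size are likely to be small, so a single event assigned differently can visibly change a column.

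**Working it through.** The documents give no SAE count or rate, so there is no figure of the plan's to reproduce. The check compares the windows and then bounds the possible size.

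**Windows for the by-arm double-blind SAE tables**

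| Rule | Start | End |
|---|---|---|
| SAE definition (SAP 2.1.2) | informed consent | end of study |
| Treatment-emergent definition (SAP 2.1.2) | first dose | 112 days after end of study drug |
| Table 4, double-blind phase (SAP 2.1.1) | after first dose | day before first open-label dose; otherwise the earlier of end of study and last dose + 84 days |

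A patient whose first SAE falls before Study Day 1 has no valid time at risk: the time until the first event would end before the window opens.

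**Can pre-dose SAEs be in the data?** Yes. Protocol 7.2.2 requires SAE reporting from consent, and Table 6-1 marks SAE collection at Visits 1 and 2. Protocol 7.1 sends screening and baseline events to medical history, but that does not cancel the explicit SAE collection.

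**Inputs.** Screening lasts 0 to 2 weeks, baseline 4 weeks and double-blind treatment 12 weeks (SAP 1.1). The planned size is 110 per arm (SAP 3). The SAE rate is an assumption, held constant over time.

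**Share of SAEs from consent to Week 12 that are pre-dose**
- 4 / (4 + 12) = 25%
- 6 / (6 + 12) = 33%

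**Inflation of the rate** if pre-dose events are counted but only post-dose time is in the denominator: (pre-dose weeks + 12) / 12
- (4 + 12) / 12 = 1.33
- (6 + 12) / 12 = 1.50

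With only serious treatment-emergent AEs in the numerator, the factor is 1.0.

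**Expected events per arm**
- Pre-dose time: 110 × 4 / 52 = 8.5 to 110 × 6 / 52 = 12.7 patient-years.
- Time at risk: 110 × 12 / 52 = 25.4 patient-years.
- The chance of at least one pre-dose SAE in either arm is 1 − exp(−2e), where e is the expected pre-dose count per arm.

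| Assumed SAEs per 100 patient-years | Pre-dose, per arm | On treatment, per arm | Chance of at least one pre-dose SAE in either arm |
|---|---|---|---|
| 2 | 0.17–0.25 | 0.51 | 29–40% |
| 4 | 0.34–0.51 | 1.02 | 49–64% |
| 8 | 0.68–1.02 | 2.03 | 74–87% |

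**Effect on the comparison.** Let a1 and a0 be the expected on-treatment counts in two arms of equal size, and b the expected pre-dose count, which is the same in both by randomisation.
- Difference: (a1 + b) − (a0 + b) = a1 − a0, which is unchanged.
- Ratio: (a1 + b) / (a0 + b), which moves toward 1. For example, suppose the true ratio is 2 and the pre-dose rate equals the placebo rate. The ratio then becomes (2 × 12 + 4) / (12 + 4) = 1.75, or (2 × 12 + 6) / (12 + 6) = 1.67.

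**The case against.** The strongest answer is that the SAP already contains the rule. Table 4 is introduced as applying to safety analyses summarised by study phase, and the tables in question are specified for the double-blind epoch. SAP 2.1.1 defines both the incidence and the exposure-adjusted rate for events in a given period. On that reading, the entry in SAP 2.1.2 only says which events are SAEs, and Table 4 selects the phase. Using Table 4 for the denominator but not for the numerator would then be an inconsistent use of one table. Protocol 9.5.2 also asks for treatment-emergent AEs by arm. The entries for fatal AEs and for AEs leading to withdrawal lack the treatment-emergent label too, which may be shorthand. The table of treatment-related AEs does carry the label, so not every table is affected.

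This reading is plausible and limits the point to a conflict. It does not remove it, because no sentence says that Table 4 governs SAEs and the exception for SAEs points the other way.

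Three further objections stand. The safety set requires a dose (SAP 2.2), so SAEs of screen failures never reach an arm column, and a serious event before randomisation may itself keep a patient out; the constant-rate figures are therefore upper bounds. SAP 2.7 plans no statistical tests on safety data. The AE form flags events that started before the first dose, so they can be identified.

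**Conclusion.** The SAP gives conflicting windows for the by-arm double-blind SAE tables and does not say which one applies. Under the SAE definition and the exception in the time-at-risk paragraph, pre-dose SAEs of dosed patients and open-label SAEs could enter the double-blind columns. The exposure-adjusted SAE rate would then divide events from one period by time from another. From pre-dose events alone, the inflation is at most about 1.33 to 1.5 times under an assumed constant rate, and probably smaller because only randomised, dosed patients count.

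A reader might infer that the plan will certainly charge pre-dose SAEs to an arm. The documents do not support this, because Table 4 and the period-based incidence definitions allow the opposite reading. A reader might also infer that the safety comparison is biased toward one arm or is generally pulled toward no difference. That is not supported either. Pre-dose events balance in expectation, so the expected risk difference is essentially unchanged. What remains is an inflated rate, a diluted ratio and chance imbalance from a few events. The efficacy analyses are not affected.

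**What to change.** - In SAP 2.7.1, replace 'serious AEs' by 'serious treatment-emergent AEs' in the by-arm double-blind tables and in the exposure-adjusted rate.
- Count events and time at risk over one stated window. It starts at the first dose and, for patients who enter open label, ends before the first open-label dose.
- In SAP 2.1.1, delete the exception for SAEs from the time-at-risk paragraph.
- Reconcile the 84-day end in Table 4 with the 112-day end of the treatment-emergent definition. Pointing to Table 4 as it stands would drop serious treatment-emergent AEs on days 85 to 112 after the last dose in patients who do not enter open label.
- List SAEs before the first dose, and any others outside the window, separately, so that no safety information is lost.

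The cost is SAP wording and one extra listing. The term needed is already defined in SAP 2.1.2, and the change brings the tables into line with Protocol 9.5.2.

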2.1.3 Study Dates

Informed Consent Date

The date on which subject signs the informed consent form.

eDiary Device Assignment Date

The date on which an eDiary device is assigned to a subject for the first time after completion of initial screening at week -4 visit.

Randomization (Enrollment) Date in DBTE

Randomization (Enrollment) Date in DBTE is the date on which a subject is assigned to one of the treatments through IRT in DBTE.

First IP Dose Date

First IP Dose Date is the date on which a subject is administered the first dose of investigational product following randomization, which may be the same day or after the randomization date. For subjects who are randomized but not dosed with double-blind IP after randomization, First IP Dose Date is considered missing.

Last IP Dose Date

Last IP Dose Date for each subject is defined as the latest date IP is administered.

End of IP Admin Date

End of IP Admin for each subject is defined as the date the decision was made to end IP as recorded on the End of IP eCRF page.

Subject-level End of Study (EoS) Date

End of study (EoS) date for each subject is defined as the last date on which the subject participated in the study.

Primary Completion Date

The Primary Completion Date is the date Double-Blind Treatment Study Completion Form for the last subject who completes DBTE.

Study Completion Date

The Study Completion Date is the EoS date of the last subject in the study.

